**2.3.2. Benefit Assessment****2.3.3. Overall Benefit: Risk Conclusion**

Potential medical benefit may be derived for participants randomised to the nitrofurantoin arm as this is a recommended treatment for uUTI. Participants randomised to the GSK3882347 arm in this study may not receive any therapeutic benefit as the efficacy profile is unknown. This is a blinded study and Investigator and Participant will not know the randomised treatment assignment. All the participants will be contributing to the development of a potential novel therapy in an area of unmet need.

The anticipated benefits of GSK3882347 are its use will not contribute to the rising resistance rates observed with conventional antibiotic therapies, and, due to its narrow spectrum of activity and mode-of-action, minimal dysbiosis is anticipated.

**3. OBJECTIVES AND ENDPOINTS AND/OR ESTIMANDS**

Objectives	Endpoints
Primary	

 
To assess the microbiological efficacy of GSK3882347 at the Test of Cure (ToC) visit in participants with uUTI who have qualifying E. coli at baseline
 
	
 
Microbiological response at the ToC Visit
 

Secondary	

 
To evaluate the safety and tolerability following CCI oral dosing for 5 days of GSK3882347 in participants with uUTI
 
	
 
Occurrence of adverse events (AEs) and serious adverse events (SAEs)
 
Clinically significant changes from baseline in laboratory values (hematology, chemistry and urinalysis), vital signs and 12lead electrocardiogram (ECG) readings at each visit
 

 
To evaluate the plasma and urine pharmacokinetic (PK) concentrations following CCI oral dosing for 5 days of GSK3882347 in participants with uUTI
 
	Plasma: 
 
GSK3882347 concentration
 
 Urine 
 
Urine concentration at 22-24h interval collection post-dose
 

Exploratory*	
CCI	

Objectives	Endpoints

CCI
 

	

\* Details regarding the exploratory analyses will be described in the statistical analysis plan (SAP). Some exploratory data may not be available until after the main database lock and may be analysed/reported separately.

### Estimands for Primary Endpoint

The primary clinical question of interest is: *What is the microbiological response for GSK3882347 assessed at ToC in participants with acute uUTI caused by E. coli uropathogens at Baseline who completed the planned course of treatment (5 days) and had no major deviations from protocol that would prevent evaluation of efficacy (as defined in the Study Deviation Rules Document). Use of rescue medication will be set to non-responder in the endpoint definition*

The Primary estimand is described by the following attributes:

- Population: Female participants with acute uUTI with a qualifying baseline *E. coli* uropathogen (Section 10.8) at baseline who completed the planned course of treatment (5 days) and had no major deviations from protocol that would prevent evaluation of efficacy
- Treatment condition: GSK3882347 CCI given orally CCI for 5 days
- Variable: Microbiological response at ToC visit
- Summary measure: Frequency and percentage of participants with microbiological response (responder/non-responder) in GSK3882347 treatment group
- Main intercurrent events anticipated:
  - Use of rescue medication prior to ToC visit- Composite strategy
  - This intercurrent event is captured through the definitions of microbiological response (see Section 9.3.2) and will be considered as non-responders.
  - Participants who are lost to follow-up prior to ToC, have a missing/unevaluable sample at ToC, discontinue study treatment due to any reason (withdrawal of

consent/AEs/missed doses) will not be included in the analysis and may be replaced at the discretion of the Sponsor.

- Rationale for estimand:

Use of rescue medication may impact microbiological outcomes, therefore, the definition of a successful microbiological response precludes the use of rescue medications. In this small, early phase, proof of mechanism study, interest lies in the treatment effect of participants who completed the planned course of treatment and follow important components of the study protocol.

Details of supportive estimands may be provided in the SAP.

### Estimand for Secondary Endpoints

The secondary clinical questions of interests are,

1. *To evaluate the safety and tolerability following CCI oral dosing for 5 days of GSK3882347 in adult female participants with uUTI*

The estimand is described by the following attributes:

- Population: Female participants with acute uUTI.
  - Treatment condition: GSK3882347 CCI given orally CCI for 5 days.
  - Variables:
    - Occurrence of adverse events (AEs) and serious adverse events (SAEs)
    - Clinically significant changes from baseline in laboratory values (haematology, chemistry and urinalysis), vital signs and 12 lead electrocardiogram (ECG) readings at each visit.
  - Summary measure: Frequency and percentages for AEs, SAEs, laboratory values, vital signs and ECG values.
  - Main intercurrent events anticipated:
    - Use of rescue medication -While on treatment strategy
      - Rescue medication could influence safety reporting and therefore, only safety data while participants are taking the study intervention will be considered for the analysis.
    - Discontinuation from the treatment due to any reasons (withdrawal of consent /AEs (if not part of the endpoint definition, for e.g., in AE and SAE)/missed doses)-Treatment policy strategy
      - The occurrence of this intercurrent event is considered irrelevant in evaluating safety, as interest lies in the full safety profile.
2. *To evaluate the plasma and urine PK parameters following CCI oral dosing for 5 days of GSK3882347*

The estimand is described by the following attributes:

- Population: Female participants with acute uUTI
- Treatment condition: GSK3882347 given orally CCI for 5 days
- Variables:
  - Plasma:
    - CCI: AUC(0-inf), Cmax, and tmax collected on Day 1
    - CCI Day 5 AUC (0-24), Cmax, and tmax collected following 5th dose, pre-dose Ctau and AUC(0-tau)
    - Urine:
      - Urine concentration at 22-24h collection following dose on Day 1 and Day 5, as data permit
      - Amount excreted in urine (Ae) of unchanged GSK3882347, fraction of the dose excreted in urine (fe), and renal clearance (CLr), as data permit.
- Summary measure: Mean, 95% confidence interval (CI), standard deviation (SD), median, minimum and maximum for non-transformed data of all PK parameters. Geometric mean, 95% CI of geometric mean, SD and coefficient of variation (CV) of geometric mean, for log transformed data for all PK parameters except for Tmax.
- Main intercurrent events anticipated:
  - Use of rescue medication
  - Discontinuation from the treatment due to any reasons (AEs/withdrawal of consent/missed doses)

All these intercurrent events will be handled using while on treatment strategy as PK data will be collected only when participants are on treatment.

## 4. STUDY DESIGN

### 4.1. Overall Design

- This Phase 1b study is a double-blind, double-dummy, nitrofurantoin-controlled study, designed primarily to evaluate microbiological response at the ToC visit and safety, tolerability and PK response following CCI oral dosing for 5 days of GSK3882347 in adult female participants with uUTI. Nitrofurantoin will be included in the study to ensure unbiased reporting of safety events. Clinical resolution and clinical symptom score will be part of the exploratory objectives of this proof of mechanism study. A detailed review of the microbiological characterization and time to response will also be explored. Aside from microbiological characterization no formal statistical comparisons of GSK3882347 and nitrofurantoin are planned.  
CCI  
All participants who provide informed consent and meet the study entry criteria will be randomized to receive either CCI GSK3882347 or 100 mg BID nitrofurantoin in a 3:1 ratio. Safety assessments will be conducted throughout the study duration; pre-treatment and post-treatment urine and

plasma PK collections will be performed and appropriate microbiological, clinical CCI assessments will also be conducted.

- As this is a first in patient study in women with uUTI, who are essentially otherwise healthy, it was considered a high patient burden to ask all participants to remain in-house for the duration of dosing. Further considerations in the study design included a lack of sites where the study could be run plus the recruitment challenges that mandating an in-house stay would bring. As it is not considered necessary to obtain full PK profiles from every study participant, and to ease participant burden, there will be 2 participant cohorts in the study:
  - Cohort 1 is an inpatient cohort: For this cohort, intensive PK sampling will be conducted during the intervention period and more frequent analyses of microbiological and clinical response to therapy will be assessed.
  - Cohort 2 is an outpatient cohort: The PK, microbiological, and clinical responses to therapy will be assessed less frequently in this cohort.
- It is anticipated that there will be a limited number of Study Sites permitted to recruit Cohort 1, these Sites may also be allowed to enroll Cohort 2 at the same time, as agreed by GSK.
- Participants will consent using the materials corresponding to the cohort they are joining, either Cohort 1 or Cohort 2.
- If at any time during the study, participants experience new or worsening signs and symptoms of UTI, they will be assessed (at site visits or in discussion over telephone, see SoA) and treated per the investigator's judgment.
- The screening period can be up to 24 hours prior to the first day of dosing. The Treatment period will consist of 5 days.
  - Cohort 1 participants will be discharged from the clinic on Day 6 and asked to return for the ToC visit 5-8 days following the last day of dosing. Participants will be asked to attend a Follow-up Visit ~28 days after the start of Treatment. The duration of the study will be approximately 28 days.
  - Cohort 2 participants will attend outpatient visits on Days 1, 2, and 6 and asked to return for the ToC visit 5-8 days following the last day of dosing. Participants will be asked to attend a Follow-up Visit ~28 days after the start of Treatment.

For treatment discontinuation and participant withdrawal, see discontinuation criteria section.

CCI

CCI

## 4.2. Scientific Rationale for Study Design

This Phase 1b study is designed primarily to evaluate microbiological response of GSK3882347 in female participants with uUTI. The sample size is not sufficiently large to enable firm conclusions to be made around therapeutic efficacy (clinical and microbiological outcomes and response) in relation to Standard of Care (SoC). However,

it will provide a preliminary assessment of the microbiologic efficacy of GSK3882347 in this patient population. This is important to establish prior to initiating larger Phase 2/3 studies.

As this will be the first study to evaluate GSK3882347 in females with UTI, safety is a key secondary endpoint for the study. The safety of GSK3882347 has previously been evaluated in one FTIH study (212148) and no safety issues were observed; there are no additional safety concerns with this proposed study in participants with ongoing uUTI infection. CCI

CCI (see Section 4.3), CCI  
CCI

Due to the specificity of GSK3882347 for *E. coli*, it is anticipated that its use will not lead to the dysbiosis caused by other treatments which also eradicate other genera such as *Lactobacillus*, which are important in maintaining gut homeostasis and are protective against UTI. This in turn should lead to reductions in the overgrowth of bacteria and yeast in the vagina, e.g. *Candida albicans* which is a common consequence of antibiotic therapy and can itself lead to long term issues with recurrence. CCI

### 4.3. Justification for Dose

#### GSK3882347

The oral GSK3882347 dose in this study is CCI CCI for 5 days. A 5-day dosing duration is in alignment with current treatment guidelines for efficacious antibacterial treatment of uUTI in women, which typically ranges from 3 to 7 days [Gupta, 2011, NICE, 2018, EAU, 2024]. The safety and tolerability of oral doses up to CCI CCI CCI has been evaluated in Phase 1 Study 212148 and there were neither SAE reports nor clinically significant changes in the laboratory data, vital signs, or electrocardiogram. All reported AEs were mild/moderate in intensity and had fully resolved by the time of participant discharge from the study.

CCI  
CCI  
CCI  
CCI  
CCI  
CCI  
CCI  
CCI  
CCI

CCI  
CCI  
CCI  
CCI However, unlike traditional antibiotics, GSK3882347 is a novel, bacterial attachment inhibitor for which translation from the murine acute cystitis model has not been validated in patients with acute uUTI. CCI  
CCI  
CCI  
CCI Given that the bladder is the site of action of GSK3882347, the use of GSK3882347 urine PK data is appropriate for selecting the GSK3882347 CCI CCI oral dose for 5 days for study in the treatment of participants with uUTI.

CCI  
CCI  
CCI  
CCI  
CCI

Mean plasma exposure following a dose of CCI × CCI was below the safety margin established in the rat 14-day GLP toxicity study, No-observed-adverse-effect Level (NOAEL) of CCI/kg/day. There was 4-fold and 3-fold coverage for Day 1 and Day 7 AUC(0-24), respectively; there was 3.4-fold and 3.1-fold coverage to the Day 1 and Day 7 Cmax, respectively.

CCI  
CCI  
CCI

### Nitrofurantoin (Macrobid)

The oral nitrofurantoin dose in this study is 100 mg BID, a total daily dose of 200 mg, for 5 days. The label indicates, for treatment of uUTI caused by susceptible strains of *E. coli* or *S. saprophyticus*, in adults and paediatric patients over 12 years of age, a 100 mg BID dose for up to 7 days (refer to locally approved prescribing information). The labelled 7-day dosing duration of nitrofurantoin was based on clinical registration studies from several decades ago. More recently, a 5-day dosing duration of nitrofurantoin was shown to be efficacious for the treatment of uUTI in women [Gupta, 2007] and a treatment duration of 3-5 days for nitrofurantoin is in alignment with current treatment guidelines [Gupta, 2011, NICE, 2018, EAU, 2024].

## 4.4. End of Study Definition

The end of the study is defined as the date of the last visit of the last participant in the study it is expected to be the last scheduled procedure shown in the Schedule of Activities for the last participant in the study at the Follow-up Visit.

A participant is considered to have completed the study if all periods of the study up to and including the Follow-up Visit have been completed.

## 5. STUDY POPULATION

Prospective approval of protocol deviations to recruitment and enrollment criteria, also known as protocol waivers or exemptions, is not permitted.

**Note:** Enrolled means a participant's, or their legally acceptable representative's, agreement to participate in a clinical study following completion of the informed consent process and screening. Potential participants who are screened for the purpose of determining eligibility for the study, but do not participate in the study, are not considered enrolled, unless otherwise specified by the protocol. A participant will be considered enrolled if the informed consent is not withdrawn prior to participating in any study activity after screening.

### 5.1. Inclusion Criteria

Participants are eligible to be included in the study only if all of the following criteria apply:

#### Age

- a. Participant must be  $\geq 18$  years of age and  $\leq 70$  years of age at the time of signing the informed consent.

#### Type of Participant and Disease Characteristics

- b. The participant has 2 or more of the following clinical signs and symptoms of uUTI with onset  $< 96$  hours of the screening assessment: dysuria, frequency, urgency, or lower abdominal pain.
- c. The participant has nitrite OR pyuria ( $\geq 10$  WBC/mm^3 OR  $> 5$  WBC/HPF OR the presence of at least 2+ leukocyte esterase) from a pre-treatment clean-catch midstream urine sample based on local laboratory procedures.

#### Weight

- d. Body mass index (BMI)  $\geq 19.0$  kg/m^2.

#### Sex and Contraceptive/Barrier Requirements

- e. A female participant is eligible to participate if she is not pregnant or breastfeeding, and one of the following conditions applies:
    - Is a woman of non-childbearing potential (WONCBP) as defined in Section 10.4: Contraceptive and Barrier Guidance.
- OR
- Is a woman of childbearing potential (WOCBP) and using a contraceptive method that is highly effective, with a failure rate of  $< 1\%$ , as described in Section 10.4 during the study intervention period and for at least 3 days after the

last dose of study intervention or 5 days after the last dose of study intervention for WOCBP choosing hormonal contraceptives (including double barrier contraception as stated in Section 10.4). The investigator should evaluate potential for contraceptive method failure (e.g., noncompliance, recently initiated) in relationship to the first dose of study intervention.

- A WOCBP must have a negative highly sensitive pregnancy test (urine as required by local regulations) before the first dose of study intervention. See Section 8.2.5 Pregnancy Testing
- Additional requirements for pregnancy testing during and after study intervention are located in Section 8.2.5.
- The investigator is responsible for review of medical history, menstrual history, and recent sexual activity to decrease the risk for inclusion of a woman with an early undetected pregnancy.

### Informed Consent

- f. Capable of giving signed informed consent as described in Section 10.1.3 which includes compliance with the requirements and restrictions listed in the ICF and in this protocol.

## 5.2. Exclusion Criteria

Participants are excluded from the study if any of the following criteria apply:

### Medical Conditions

1. Positive highly sensitive urine pregnancy test at screening.
2. Women that are currently lactating and or breast feeding.
3. The participant has a BMI  $\geq 40.0$  kg/m^2 or a BMI  $\geq 35.0$  kg/m^2 with obesity-related health conditions such as high blood pressure or uncontrolled diabetes (defined as a non-fasting glucose value  $>300$  mg/dL or based on investigator judgment).
4. The participant is immunocompromised or has altered immune defenses that may predispose the participant to a higher risk of treatment failure and/or complications (e.g., renal transplant recipients, participants with clinically significant persistent granulocytopenia [absolute neutrophil count  $<1000/\mu\text{L}$ ], and participants receiving immunosuppressive therapy, including corticosteroid therapy [e.g.  $\geq 40$  mg/day prednisolone or equivalent for  $>1$  week or; prednisolone or equivalent  $\geq 20$  mg/day for  $>2$  weeks or; prednisolone or equivalent  $\geq 10$  mg/day for  $>6$  weeks]).
5. The participant has any surgical or medical condition (active or chronic) that may interfere with drug absorption, distribution, metabolism, or excretion of the study intervention (e.g., ileostomy or malabsorption syndrome). Participants who have had a gastric bypass or a cholecystectomy are excluded from the study.
6. The participant has uUTI that is known or suspected to be due to fungal, parasitic, or viral pathogens; or known or suspected to be due to *Pseudomonas aeruginosa* or any

Enterobacterales other than *E. coli* [REDACTED] as the contributing pathogen.

7. The participant has symptoms known or suspected to be caused by another disease process, such as asymptomatic bacteriuria, overactive bladder, chronic incontinence, or chronic interstitial cystitis, that may interfere with the clinical efficacy assessments.
8. The participant has an anatomical or physiological anomaly that predisposes the participant to UTIs or may be a source of persistent bacterial colonization, including calculi, obstruction or stricture of the urinary tract, primary renal disease (e.g., polycystic renal disease), or neurogenic bladder, or the participant has a history of anatomical or functional abnormalities of the urinary tract (e.g., chronic vesicoureteral reflux, detrusor insufficiency).
9. The participant has an indwelling catheter, nephrostomy, ureteral stent, or other foreign material in the urinary tract.
10. The participant who, in the opinion of the investigator, has an otherwise complicated UTI, an active upper UTI (e.g., pyelonephritis, urosepsis), signs and symptoms onset  $\geq 96$  hours before the screening assessment, or a temperature  $\geq 101^\circ\text{F}/38^\circ\text{C}$ , flank pain, chills, or any other manifestations suggestive of upper UTI.
11. The participant has anuria, oliguria, or significant impairment of renal function ( $\text{eGFR} < 60 \text{ mL/min/1.73m}^2$  [calculated using CKD-EPI 2021; [Inker, 2021](#)] or serum creatinine  $> 1.5 \times$  upper limit of normal [ULN] at screening). Note: *Please reference the Study Reference Manual for guidance on calculating the eGFR during screening.*
12. The participant presents at enrollment with a suspected sexually transmitted infection.
13. The participant has congenital long QT syndrome or known prolongation of the corrected QT (QTc) interval.
14. The participant has uncompensated heart failure, defined as New York Heart Association Class  $\geq \text{III}$ .
15. The participant has severe left ventricular hypertrophy.
16. The participant has a family history of QT prolongation or sudden death.
17. The participant has a recent history of vasovagal syncope or episodes of symptomatic bradycardia or bradyarrhythmia within the last 12 months.
18. The participant has a QTc  $> 450$  msec or a QTc  $> 480$  msec for participants with bundle-branch block. **Note:** The QTc is the QT interval corrected for heart rate according to Fridericia formula, machine, or manual overread.
19. The participant has an alanine transferase (ALT) value  $> 2 \times \text{ULN}$ .
20. The participant has a bilirubin value  $> 1.5 \times \text{ULN}$  (isolated bilirubin  $> 1.5 \times \text{ULN}$  is acceptable if bilirubin is fractionated and direct bilirubin  $< 35\%$ ).
21. The participant has a current or chronic history of liver disease or known hepatic or biliary abnormalities (with the exception of Gilbert's syndrome or asymptomatic

gallstones), including viral hepatitis or moderate-to-severe liver insufficiency (Child Pugh class B or C).

22. History of positive human immunodeficiency virus (HIV) antibody or antibody/antigen test.
23. History of presence of Hepatitis B surface antigen (HBsAg) within 3 months prior to first dose of study intervention.
24. History of Hepatitis C antibody test result within 3 months prior to first dose of study intervention.
- **NOTE:** Participants with a history of a positive Hepatitis C antibody due to prior resolved disease can be enrolled, only if there is a history of a confirmatory negative Hepatitis C ribonucleic acid (RNA).
25. History of a Positive Hepatitis C RNA test result within 3 months prior to first dose of study intervention.
26. Substance abuse: Active substance abuse or a history of substance abuse (in the opinion of the Principal Investigator) within 6 months prior to the initial Screening visit. Note that *documented* medical use of marijuana or occasional recreational use of marijuana is permitted.
27. A positive confirmation of COVID-19 infection, or high clinical index of suspicion for COVID-19.
28. The participant has a history of significant cardiac, endocrinologic, haematologic, pulmonary, metabolic, renal (including significant or chronic proteinuria, but excluding transient proteinuria in the setting of infection), hepatic, immunologic, urologic, neurologic, dermatologic, psychiatric or gastrointestinal conditions that, in the opinion of the investigator places the participant at unacceptable risk or would make adhering to study procedures for the duration of the study difficult.

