### **8.2.2. Vital Signs**

- Vital signs (to be taken before blood collection for laboratory tests) will include tympanic-measured temperature, pulse and respiratory rate, systolic and diastolic blood pressure.
- Blood pressure and pulse measurements will be assessed in a semi-supine or seated position (dependant on site standard practice) with a completely automated device. Manual techniques will be used only if an automated device is not available. (consistency of assessment at each site is requested for each participant throughout the study)
- Blood pressure and pulse measurements should be assessed after at least 10 minutes of rest for the participant in a quiet setting without distractions (e.g., television, cell phones).

- Blood pressure measurements and pulse, when measured in triplicate as in the SoA, will consist of 3 consecutive readings recorded at intervals of at least 1 minute and the average of the 3 readings will be recorded on the CRF.

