### **9.1. Statistical Hypotheses**

No formal statistical hypotheses will be tested in this study.

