Fever: oral	37.7 to 38.5°C or 100.0 to 101.5°F	38.6 to 39.5°C or 101.6 to 102.9°F	39.6 to 40.5°C or 103 to 105°F	>40°C or >105°F
Fatigue	Normal activity reduced <48 hours	Normal activity decreased 25 to 50%; >48 hours	Normal activity decreased >50%; cannot work	Unable to care for self

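### Exclusion criterion 10 prints one fever limit as two temperatures 0.33°C apart, so eligibility between 38.0°C and 38.33°C depends on which figure is applied

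*Protocol*

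**What the plan says.** Exclusion 10 in Protocol section 5.2 opens with "The participant who, in the opinion of the investigator, has an otherwise complicated UTI, an active upper UTI (e.g., pyelonephritis, urosepsis" and goes on to list symptom onset 96 hours or more before screening, a temperature limit and further signs. The temperature limit and the items after it read "\geq 101^\circ\text{F}/38^\circ\text{C}$ , flank pain, chills, or any other manifestations suggestive of upper UTI". The items are joined by "or", and section 5.2 excludes a woman if any one criterion applies.

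Three other places bear on how the limit is applied:

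- Section 8.2.2 lists the vital signs as "tympanic-measured temperature, pulse and respiratory rate, systolic and diastolic blood pressure". It gives the measurement site but no scale.
- Section 5 states: "Prospective approval of protocol deviations to recruitment and enrollment criteria, also known as protocol waivers or exemptions, is not permitted".
- The benefit-risk conclusion (section 2.3.3) says that participants on GSK3882347 "may not receive any therapeutic benefit as the efficacy profile is unknown". Allocation to that arm is 3:1.

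The eligibility temperature is not restated or explained anywhere else in the protocol or the SAP.

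**The concern.** A limit given in two scales should be one limit. Here the slash presents 101°F and 38°C as equivalent, and they are not. For a narrow range of readings the criterion gives two answers, and the site has no rule for choosing between them. This does not require sites to use different thermometers: one reading of 38.1°C, which is 100.6°F, meets one printed figure and fails the other at the same site.

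The entry screen is what is at stake. Fever is listed among the signs of upper infection, and three of every four randomised women receive an agent whose efficacy the protocol calls unknown. There is also a bookkeeping consequence. A site applying one figure could enrol a woman in good faith, and a monitor applying the other could record an eligibility deviation.

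**Working it through.** **Inputs.** Two figures from exclusion 10: 101°F and 38°C, both with the sign ≥. No other trial quantity enters. The protocol states "No formal statistical hypotheses will be tested in this study", and no sample size or error rate depends on this limit.

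**Formulas.** C = (F − 32) × 5/9 and F = C × 9/5 + 32.

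**Can the printed pair be reproduced?**

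- Fahrenheit to Celsius: (101 − 32) × 5/9 = 38.33°C. To whole degrees this is 38°C, which matches the print.
- Celsius to Fahrenheit: 38 × 9/5 + 32 = 100.4°F. To whole degrees this is 100°F, which does not match the printed 101°F.

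The pair agrees only if the Celsius figure is taken as 38.33 rounded down. That is a plausible origin, but the criterion does not say so.

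**Size of the gap.** 38.33 − 38.00 = 0.33°C; 101 − 100.4 = 0.6°F.

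**Which readings are affected?**

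| Reading | Meets ≥38°C | Meets ≥101°F | Result |
|---|---|---|---|
| Below 38.0°C (below 100.4°F) | No | No | Figures agree |
| 38.0°C to below 38.33°C (100.4°F to below 101°F) | Yes | No | Figures conflict |
| 38.33°C (101°F) and above | Yes | Yes | Figures agree |

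On a thermometer reading to 0.1 degree, the conflict covers 38.0, 38.1, 38.2 and 38.3°C (38.3°C is 100.94°F), or 100.4 to 100.9°F.

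**Does another passage settle it?** The only other paired fever values are in the adverse-event toxicity table (section 10.7), where grade 1 is "37.7 to 38.5°C or 100.0 to 101.5°F". That row grades oral temperature, whereas the study measures tympanic temperature. Its own pairs are also approximate: 38.5 × 9/5 + 32 = 101.3°F against a printed 101.5°F, and 37.7 × 9/5 + 32 = 99.86°F against a printed 100.0°F. It cannot serve as a conversion standard for eligibility.

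**The case against.** The best case against the point is that the criterion does not hang on the number. It rests on the investigator's opinion, and flank pain, chills or any other sign of upper infection also exclude. A woman at 38.1°C whom the investigator suspects of pyelonephritis stays out on either scale. The no-waiver rule binds sites to these clauses as much as to the number. This stands, and it limits the consequence. It does not remove the conflict for a woman whose only such sign is the temperature.

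A second argument is that a literal reader would treat the two figures as alternatives, so that meeting either one excludes. That reading is possible. It would, however, make the 101°F figure redundant, because every reading at or above 101°F is already above 38°C. The text does not choose it.

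A third is that the Study Reference Manual may name a governing unit. It is not among the documents, so this is unknown.

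A reader might go further and infer that the same febrile woman is excluded at one site and dosed at another. The documents do not support this as fact. They do not say which scale any site uses, and only the narrow band is affected, not fever in general. Nor is the temperature the criterion's only numeric limit, since the 96-hour onset rule is in the same sentence.

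**Conclusion.** The inconsistency is real and rests on unit conversion alone. Exclusion 10 contains two cut-offs, 0.33°C (0.6°F) apart. A woman with a reading from 38.0°C to below 38.33°C can be excluded or admitted depending on the figure applied, if nothing else leads the investigator to exclude her.

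The number of women affected cannot be derived, because the documents give neither a distribution of screening temperatures nor the scale used at each site. A reader might also infer that the primary result is distorted. The documents do not show that: no endpoint definition uses this temperature, and which deviations remove a woman from the Micro-MPP set is left to a separate deviation rules document. After entry, the protocol provides for worsening symptoms to be assessed and treated at any time (section 4.1) and allows rescue medication throughout (section 6.8.3).

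This is a narrow error in an operative eligibility limit with a safety purpose. It is worth correcting because the correction is small and makes the entry screen uniform.

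**What to change.** The sponsor should reconcile the two figures in exclusion 10: decide which temperature is intended and print that single limit with its exact conversion in the other scale. The same value should be used wherever eligibility is checked. Which temperature is right is a clinical decision for the sponsor, and this review takes no position on it.

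The cost is one corrected line in the protocol and in any site material that repeats it. Amendment 4 made a similar correction to exclusion 11, where the units did not belong to the quantity named. The downside is that, depending on the value chosen, a few women are newly excluded or newly admitted. If enrolment has already taken place under the present text, women with screening readings in the band should be identified, so that whether a deviation occurred is decided once and in the same way for all of them.
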